6.2 Safety Data

The definitions and requirements in relation to adverse events are described in Section 8. All adverse events (AEs), including serious adverse events will be assessed by the Investigator according to Common Terminology Criteria for Adverse Events (CTCAE v 5.0) (see Appendix 5: Grading of adverse events) and documented up until 4 weeks after the final dose of study medication i.e. Follow-up visit.

Planned hospital admissions and/or surgical operations for an illness or disease which existed before the drug was given or the participant was randomized into the clinical study will not be considered adverse events.

6.2.1 Evaluations of Specific AEs

Known topical rapamycin adverse events will be compared between groups:

- Treatment area irritation (e.g. erythema, papules, vesicles, erosion etc.)
- Treatment area dryness

Known oral rapamycin adverse events will be compared between groups:

- Hypersensitivity reactions
- Angioedema

- Fluid retention
- Wound healing disturbance
- Hyperlipidemia
- Renal function decline
- Proteinuria
- Infections

CRFs will not specifically list these adverse events but they will be separated for analysis.

6.2.2 Overall Evaluation of Safety

The overall evaluation of safety throughout the trial will be based on all adverse events observed during the Treatment Phase and Follow-Up.

A physical exam, vital signs and laboratory tests (hematology, biochemistry, lipid panel and urinalysis) will be conducted during screening (baseline results), at each subsequent visit (V1-V5) and at follow-up. Clinically significant changes to the test results from baseline will be evaluated and compared among the three study groups. If participants are unable to provide blood samples at all timepoints, the minimum to be collected should be samples at screening, V1 or V2 and V5.

6.2.3 Systemic absorption of rapamycin

Blood rapamycin concentrations should be measured at screening and at each subsequent visit (V1-5) and at follow-up. If participants are unable to provide blood samples at all timepoints, the minimum to be collected should be samples at screening, V1 or V2 and V5. Samples will be collected by venipuncture by a qualified member of the study team. A total of approximately 5 mL blood will be collected into a lithium-heparin vacutainer.

As blood rapamycin levels are being measured as a safety parameter (blood rapamycin levels are not anticipated to exceed immunosuppression levels of 8-20 ng/mL), samples should be analyzed at a local accredited laboratory using validated analytical methods. As blood rapamycin concentrations may be measured by various chromatographic and immunoassay methodologies, each site should use the same analytical method throughout the study.

7 EXPERIMENTAL PROCEDURE

The study is intended to be carried out over a total of up to 10 months. The study consists of a Screening Phase (up to 3 months), a Treatment Phase (baseline and 5 clinical visits; 6 months), and Follow-Up (1 month). For early withdrawals, the follow-up visit will be scheduled from the last visit where subject withdrawal was confirmed. The study assessments are summarized in Table 3.

Table 3: Schedule of Assessments

Assessment	Screening Phase			Treatment Phase						Follow-Up
	Informed consent	Screening	Randomization	V0 Baseline	V1 2 weeks	V2 8 weeks	V3 14 weeks	V4 20 weeks	V5 26 weeks	4 weeks after final dose
Tolerance	≤3 months before V0	≤14 days before V0		NA	±3 days	±3 days	±3 days	±3 days	±3 days	±5 days
Informed consent	X ¹									
Inclusion/exclusion criteria		X								
Demographic data		X								
Medical history		X								
Physical examination		X			X	X	X	X	X	X
Vital signs		X	X	X	X	X	X	X	X	X
Pregnancy test ²		X		X	X	X	X	X	X	
Hematology, biochemistry & lipid panel ³		X			X	X	X	X	X	X
Urinalysis		X			X	X	X	X	X	X
Blood rapamycin concentration ^{3,4}		X			X	X	X	X	X	X
Drug administration (once daily, evenings)				X						
Photographs of FA			X		X	X	X	X	X	X
IGA		X	X		X	X	X	X	X	X
FASI			X		X	X	X	X	X	X
Percentage improvement (subjective & objective)					X	X	X	X	X	
Categorical improvement									X ⁵	
Concomitant medications		X	X	X						X
Adverse events				X						X

¹ if more than a month passes between obtaining informed consent and randomization, then informed consent should be re-obtained

² only conducted for women of childbearing potential

³ if participants are unable to provide blood samples at all timepoints, the minimum to be collected should be samples at screening, V1 or V2 and V5

⁴ blood sampling collected prior to the daily evening dose

⁵ categorical assessment only to be done at V5, unless early withdrawal/discontinuation, in which case categorical assessment should be completed at last visit

7.1 Screening Phase

The screening phase will occur up to 3 months prior to the initial Clinical Visit (V0).

Prior to the initiation of the screening assessments, potential participants will be given a complete explanation of the study.

Informed Consent may be obtained up to 3 months prior to the initial Clinical Visit (V0), however if more than one month passes between obtaining informed consent and randomization, then informed consent should be re-obtained.

Once an individual has agreed to participate and signed a copy of the Informed Consent documents the following assessments will be performed up to 14 days prior to V0 to assess the participant's eligibility for enrolment in the study according to the Inclusion/Exclusion criteria:

- Demographic data (age, sex, height, weight etc.)
- Complete medical history - including past or present history of cardiac, pulmonary, gastrointestinal, hepatic, renal, immunological, hematological, neurological, musculoskeletal or psychiatric conditions (if any), allergy to food or drugs and medication history for the previous three months.
- Physical examination
- Vital signs (temperature, blood pressure [systolic and diastolic], pulse rate)
- Urine pregnancy tests (females of childbearing potential only)
- Hematology
 - Hemoglobin
 - Hematocrit
 - Platelet count
 - Red Blood Cell (RBC) count
 - White Blood Cell (WBC) count
 - Differential Leukocyte Count (DLC)
- Biochemistry
 - Sodium
 - Potassium
 - Urea
 - Creatinine
 - Phosphate
 - Glucose
 - Albumin
 - Total protein
 - Alkaline phosphatase

- Gamma-glutamyl transferase
- Aspartate transaminase
- Alanine transaminase
- Bilirubin
- Lipid panel
 - Total cholesterol
 - High-density lipid cholesterol
 - Low-density lipid cholesterol
 - Triglycerides
- Blood rapamycin concentration
- Urinalysis
- Clinical examination of FA lesions using the Investigators Global Assessment (IGA)
- Concomitant medications

If subjects meet all eligibility criteria, they will be assigned a unique randomization number up to two weeks before the first application of the study drug, at which time the following baseline assessments will be conducted:

- Vital signs (temperature, blood pressure [systolic and diastolic], pulse rate)
- Photographs of FA lesions
- Clinical examination of FA lesions using the Investigators Global Assessment (IGA) and Facial Angiofibroma Severity Index (FASI)
- Concomitant Medications

Photographs of FA lesions will be taken using standardized methodologies as established at each site. Photographs at each visit will be signed and dated by the Investigator. The randomization number of the patient will be recorded on the photograph along with the IGA and FASI scores determined at that visit. Photographs will not be used directly for any efficacy endpoints, but will be available for auditing purposes and may be used in publications of the study results (deidentified photographs only).

7.2 Treatment Phase

Once an individual's eligibility for the trial has been confirmed and the participant has been randomized, the Treatment Phase can start. The Treatment Phase is divided into an initial clinical Visit (V0) and 5 subsequent clinical visits (V1-5).

7.2.1 Initial Clinical Visit (V0)

During the Initial Clinical Visit (V0) the initial application of the study drug will be performed under medical supervision. The participating clinician will determine the size of facial area affected and instruct the patient the amount of product to be applied. This will be recorded in source documents.

In addition, the following assessments will be conducted:

- Vital signs (temperature, blood pressure [systolic and diastolic], pulse rate)
- Urine Pregnancy test (females of childbearing potential only)
- Concomitant Medications
- Adverse event monitoring

7.2.2 Clinical Visits 1-5 (V1-5)

During Clinical Visits (V1-5) the following assessments will be performed:

- Physical examination
- Vital signs (temperature, blood pressure [systolic and diastolic], pulse rate)
- Urine Pregnancy test (females of childbearing potential only)
- Hematology, Biochemistry, Lipid panel (as per screening assessments)
- Urinalysis
- Blood rapamycin concentration
- Confirm application of study drug from the patient diary
- Photographs of FA lesions
- Lesion severity with IGA
- Lesion severity with FASI
- Percentage Improvement since V0
 - Subjective assessment
 - Objective assessment
- Categorical Improvement (at V5 or visit when withdrawal is confirmed only)
- Concomitant medications
- Adverse event monitoring

7.3 Follow-Up Period

Patients will be invited back for a follow up visit ~28 days (4 weeks) after their final visit of the Treatment Phase (depending on participation and withdrawal status) and the following assessments will be performed:

- Physical examination
- Vital signs (temperature, blood pressure [systolic and diastolic], pulse rate)
- Hematology, Biochemistry, Lipid panel (as per screening assessments)
- Urinalysis
- Blood rapamycin concentration
- Photographs of FA lesions
- Lesion severity with IGA
- Lesion severity with FASI
- Adverse event monitoring

- Concomitant medications

8 ADVERSE EVENTS

8.1 Definitions

An adverse event (AE) is defined as any unintended, unfavorable clinical sign or symptom, any new illness or disease or deterioration of existing illness or disease, or any clinically relevant deterioration in laboratory variables (e.g., hematological, biochemical, hormonal) or other clinical tests (e.g., ECG, X-ray), whether or not considered treatment related.

Planned hospital admissions and/or surgical operations for an illness or disease which existed before using the treatment or before the participant was randomized in the clinical study will not be considered adverse events.

The severity of an adverse event will be assessed by the Investigator according to Common Terminology Criteria for Adverse Events (CTCAE v 5.0) (see Appendix 5: Grading of adverse events). The relationship of an adverse event to the use of the drug will be assessed by the Investigator as described in Appendix 5: Grading of adverse events.

Participants will be specifically asked about the expected side-effects (such as treatment area irritation, dryness and redness), as well as any other symptoms they may have experienced, at each study visit. Other important aspects include photosensitivity reactions and adverse events reported for the oral formulation of rapamycin (Rapamune) including:

- Hypersensitivity reactions (including anaphylactic/anaphylactoid reactions, angioedema, exfoliative dermatitis and hypersensitivity vasculitis)
- Angioedema
- Fluid retention
- Wound healing disturbance
- Hyperlipidemia
- Renal function decline
- Proteinuria
- Increased susceptibility to opportunistic infections (including tuberculosis, progressive multifocal leukoencephalopathy (PML), interstitial lung disease, Pneumocystis carinii pneumonia)

Participants experiencing adverse events will be followed clinically until their health has returned to baseline status or until all abnormal values have returned to normal or have otherwise been explained. The investigators will provide or arrange appropriate supportive care for the participant if necessary.

Participants will be advised to contact their doctor immediately if they develop signs or symptoms of hypersensitivity.

8.1.1 Serious Adverse Event

A serious adverse event is an AE that:

- results in death;
- results in persistent or significant disability/incapacity;
- is life-threatening (i.e. the participant was, in the opinion of the Investigator, at immediate risk of death from the event as it occurred; this does not include an event that, had it occurred in a more severe form, might have caused death);
- requires participant hospitalization or prolongs hospitalization;
- is a congenital anomaly/birth defect; or
- is another medically significant event that, on the basis of appropriate medical judgment, may jeopardize the participant and may require medical or surgical intervention to prevent one of the outcomes listed above (e.g. allergic bronchospasm requiring intensive treatment in an emergency room or home, blood dyscrasias or convulsions that do not result in hospitalization, or the development of drug dependency or drug abuse).

An adverse event fulfilling any one or more of these criteria must be reported as a serious adverse event, irrespective of the interventions given, and even if it is the result of an interaction or drug abuse.

A distinction should be drawn between serious and severe adverse events. Severity is an estimate or measure of the intensity of an adverse event, while the criteria for serious are indications of adverse participant outcomes for regulatory reporting purposes. A severe adverse event need not necessarily be considered serious and a serious adverse event need not be considered severe. For example, nausea that persists for several hours may be considered severe nausea, but not a serious adverse event. On the other hand, a myocardial infarction that may be considered minor could also be a serious adverse event if it prolonged hospitalization, for example. The severity of AEs will be graded according to Common Terminology Criteria for Adverse Events (CTCAE v 5.0).

8.1.2 Suspected Adverse Drug Reactions (ADR)

According to ICH GCP 1.1, “*all noxious and unintended responses to a medicinal product related to any dose should be considered adverse drug reactions.*”

8.1.3 Unexpected Adverse Drug Reaction

An adverse reaction, the nature or severity of which is not consistent with the applicable product information.

8.2 Procedure for Adverse Event Reporting

All adverse events (non-serious and serious) spontaneously reported by the participant and/or in response to an open question from the study personnel or revealed by observation, physical examination, or other diagnostic procedures will be recorded.

All adverse events (non-serious and serious) must be recorded on the source documents and case report forms provided by the Sponsor. The following information shall be included:

- nature of the adverse event
- the onset date of adverse event
- the end date of adverse event (if applicable)
- the outcome of the AE
- the frequency of the AE
- action taken with the investigational product
- relationship to the investigational product
- whether any treatment was received for this adverse event
- whether this adverse event was serious

Any adverse event or abnormal laboratory result evaluated as clinically significant by the study investigator shall be followed until satisfactory resolution: it becomes stable, or it can be attributed to other causes (existing conditions) and in the opinion of investigators that further follow-up is not required.

8.3 Procedure for Serious Adverse Event Reporting

8.3.1 Reporting to the Sponsor

In addition to entering each serious adverse event irrespective of causality on the appropriate page of the case report form (CRF), the Investigator must complete a Serious Adverse Event Report (SAER) for each serious adverse event regardless of causality to the investigational drug. A sample of the SAE form for reporting is presented in Appendix 6: SAE Reporting Form. The SAER must be faxed to the Drug Safety Officer at the CRO and then to AFT Pharmaceuticals Ltd ([contact]) within 24 hours of the event being notified to/realized by study site staff. The Drug Safety Officer will contact the Investigator should it be necessary to clarify any of the event information. The Investigator should provide any additional follow-up information for the event to AFT Pharmaceuticals Ltd as soon as it becomes available and up to the point the event has been resolved. This reporting requirement is applicable to serious adverse events that occur during the designated study period. If the Investigator is notified of a serious event post study that he or she determines to be causally related to study medication, the event should also be reported through this process.

8.3.2 Reporting to Local IEC and Regulatory Authorities

Serious adverse events will be reported to the local ethics committee and the relevant health authority as per the requirements.

8.3.2.1 Local Ethics Committee

There is no general requirement for applicants to submit individual or expedited reports of SAEs or suspected unexpected serious adverse reactions (SUSARs) to local ethics committees who do not have

the expertise or resources to review them. In the case of intervention studies involving a new medicine, the researcher is required to submit an annual summary of safety information.

8.3.2.2 Regulatory Authorities

Fatal or Life-Threatening Unexpected ADRs

An ADR is considered “fatal or life-threatening” if, in the review of either the investigator or sponsor, its occurrence places the participants at immediate risk of death. It does not include an adverse events of adverse drug reaction that, had it occurred in a more severe form, might have caused death.

Fatal or life-threatening ADRs occurring in clinical investigations is subject to expedited reporting. Regulatory agencies should be notified (e.g., by telephone, facsimile, transmission, or in writing) as soon as possible but no later than 7 calendar days after the first knowledge by the sponsor that a case qualifies, followed by as complete a report as possible with 8 additional calendar days. This report must include an assessment of the importance and implication of the findings, including relevant previous experience with the same or similar medicinal products.

All other serious, unexpected ADRs

Serious, unexpected reaction (ADRs) that are not fatal or life-threatening must be filed as soon as possible but no later than 15 calendar days after first knowledge by the sponsor that the case meets the minimum criteria for expedited reporting.

9 PROTOCOL DEVIATIONS

This study will be conducted, within reasonable limits, as described in this protocol, except for emergency situations in which the protection, safety, and well-being of the participant requires immediate intervention, based on the judgement of the Investigator (or a responsible, appropriately trained professional designated by the Investigator). In the event of a significant deviation from the protocol due to an emergency, accident, or mistake, the Investigator or designee must contact the Sponsor, or the Sponsor’s agent, at the earliest possible time by telephone. This will allow an early joint decision regarding the best way to proceed with the study. The Investigator and the Sponsor will document this decision. The Institutional Review Board (IRB) or Independent Ethics Committee (IEC) will be informed of all protocol changes by the Investigator in accordance with the IRB or IEC established procedure. No significant planned or deliberate deviations from the protocol of any type will be made without the Sponsor’s agreement and complying with all the IRB or IEC established procedures.

10 PLAN FOR STATISTICAL AND OTHER CALCULATIONS

10.1 Populations of Interest

The Intent-To-Treat (ITT) population will consist of all subjects who receive at least one dose of study drug. Subjects will be included in the group to which they were randomized irrespective of the treatment actually taken. The ITT population is the primary population for the efficacy analysis.

The Per-Protocol (PP) population will consist of all ITT subjects who remain in the study for at least 26 weeks (i.e. complete the double-blind treatment period) and who do not incur a major protocol violation that would challenge the validity of their data.

The safety population is the population for all safety assessments. The safety population will include all subjects who are treated with study drug. Subjects will be included in the treatment group according to the treatment actually taken.

10.2 Sample Size

This is the first randomized clinical trial of *Rapamycin cream, topical* applied to patients and the first time that the Investigator's Global Assessment (IGA) scale will be used for the assessment of the severity of facial angiofibroma.

It is anticipated that no more than 10% of the placebo group will achieve the primary endpoint, a successful treatment according to IGA scale after 26 weeks treatment and that each dose of *Rapamycin cream, topical* will achieve at least 40% successful treatment (42). Including the Holm-Bonferroni adjustment of the type I error rate for multiple comparisons ($\alpha = 0.025$), a sample size of 40 participants is required in each randomized group to achieve >80% power for these comparisons.

10.3 Statistical Analyses

10.3.1 Primary Efficacy Endpoint

The data for the primary endpoint, the percentage of patients obtaining successful treatment based on the blind assessment using the IGA scale after 26 weeks or at last visit if early withdrawal/discontinuation, will be summarized by treatment group. Success is defined as clear or almost clear with an improvement of at least two grades from baseline, i.e. 2 to 0; 3 to 1. Statistical analysis of the primary endpoint will be performed using a logistic regression model which will include treatment effect and stratum as fixed factors and baseline IGA score as a covariate. This model will be used to generate the odds ratios and 95% confidence intervals of the individual dose treatments compared with placebo, with the p-values for these comparisons adjusted using the Holm-Bonferroni adjustment.

An exploratory analysis will compare the two active groups in the same manner as the primary endpoint, with no adjustment for multiple comparisons. This analysis will be summarized with the Odds ratio and 95% confidence interval.

10.3.2 Secondary Efficacy Endpoints

The time-to-treatment success will be summarized using Kaplan-Meier analyses and compared between each dose group and placebo using the stratified log-rank test. The secondary endpoints change in IGA and FASI from baseline to 26 weeks/last assessment, and objective and subject improvement from baseline to 26 weeks/last assessment, will be summarized by treatment group using means, medians, standard deviations, interquartile ranges and minima and maxima. These changes will be analyzed using ANOVA including treatment and stratum as main effect fixed factors, with planned pairwise comparisons between each dose group and placebo. If the data is not adequately normally distributed the Kruskal-Wallis non-parametric ANOVA, and Mann-Whitney U tests comparing changes between treatment groups will be used for the analysis. Baseline for the IGA and FASI scores is defined as the last pre-treatment assessment, whether obtained at screening, randomization or V0.

Categorical Improvement scores will be compared amongst study groups using the Kruskal-Wallis non-parametric ANOVA, and Mann-Whitney U tests comparing changes between each dose group and placebo.

The type I error rate associated with the testing of the six secondary endpoints will be strictly controlled using the Hochberg procedure. This will involve ranking the 6 p-values derived from the testing of each dose group with placebo from highest to lowest. If the highest p-value is <0.05 , then all six comparisons are considered statistically significant if not significant then the next highest is tested at $p=0.025$. The p-value continues to reduce at each non-significant step based on the Bonferroni adjustment.

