4.2 Inclusion Criteria

1. Male and female patients aged ≥ 6 years and ≤ 65 years on the day informed consent is obtained
2. Patients diagnosed with TSC based on the clinical diagnostic criteria of International Tuberous Sclerosis Complex Consensus Conference 2012 and presenting visible facial angiofibroma
3. An FA severity score of 2 or 3 on the IGA scale
4. Patients or their legal representatives capable of understanding the explanation of the clinical trial and who give written informed consent for participation
5. Patients or their legal representatives able to maintain patient diaries following the instructions of the investigator or sub-investigator

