6.1.2 Secondary and Exploratory Efficacy Endpoints

The following *secondary* efficacy endpoints will be derived from IGA scores:

1. Time to treatment success
2. Change from baseline in IGA after 26 weeks treatment or at last visit if early withdrawal/discontinuation

In addition, the following *exploratory* efficacy endpoint will be derived from IGA scores:

1. The percentage of patients with successful treatment according to IGA scale after 2, 8, 14 and 20 weeks treatment
2. Change from baseline in IGA after 2, 8, 14 and 20 weeks treatment
7. Change in IGA from week 26 to Follow-up (4 weeks after final dose)

Lesion severity will also be graded using the Facial Angiofibroma Severity Index (FASI) [Appendix 2: Facial Angiofibroma severity index (FASI)]. Using the FASI, lesions are graded according to their erythema, size and extent. Erythema is scored from 0 to 3 and lesion size are scored from 0 to 3, while extent carries greater specific weight (scored from 2 to 3), as the scale's developers consider the lesion's extent to be a fundamental factor in estimating the degree of severity.

The FASI is obtained by summing the partial scores assigned to each of three relevant features of FA for a maximum score of 9. FASI was first described in a clinical trial of 9 months duration (33) and the reliability and validity was subsequently reported (16). This will provide data for the following *secondary* efficacy endpoint:

3. The change in FASI from baseline after 26 weeks treatment or at last visit if early withdrawal/discontinuation

In addition, the following *exploratory* efficacy endpoints will be derived from FASI scores:

3. Change from baseline in FASI after 2, 8, 14 and 20 weeks treatment
4. Change from baseline in each FASI component (erythema, size, extension) after 2, 8, 14, 20 and 26 weeks treatment
8. Change in FASI from week 26 to Follow-up (4 weeks after final dose)

To the extent possible, the same Investigator should conduct all FASI assessments per patient at each site throughout the study.

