At Visits 1-5 patients or their parents/caregivers (for patients under the age of 18) will be asked to estimate the percentage improvement in the FA lesion appearance from their perspective since baseline (V0) [Appendix 3: Subjective and Objective Improvement Ratings]. Similarly, the investigators will estimate the percentage improvement from a clinical perspective. Improvement will be defined as: minimal <30%, moderate 30-59%, good 60-89%, excellent >90%. This is similar to the objective and subjective improvement ratings used by Foster et al. (23) and Tu et al. (37). This will provide data for the following *secondary* efficacy endpoints:

4. Subjective improvement rating (minimal, moderate, good or excellent) in facial angiofibroma from first visit (V0) after 26 weeks of treatment or at last visit if early withdrawal/discontinuation
5. Objective improvement rating (minimal, moderate, good or excellent) in facial angiofibroma from first visit (V0) after 26 weeks of treatment or at last visit if early withdrawal/discontinuation

In addition, the following *exploratory* efficacy endpoints will be derived from percentage improvement scores:

5. Subjective (patient or parent/caregiver) improvement rating from first visit (V0) after 2, 8, 14 and 20 weeks treatment
6. Objective (clinician) improvement rating from first visit (V0) after 2, 8, 14 and 20 weeks treatment

To the extent possible, the same clinician should conduct all improvement rating assessments per patient at each site throughout the study. Similarly, the same person (patient or parent/caregiver) should report all improvement rating assessments throughout the study.

Upon completion of the double-blind treatment phase, patients or their parents/caregivers (for patients under the age of 18) will be asked which of the following statements they agree with:

- 3: I got significantly better on the treatment
- 2: I got moderately better on the treatment
- 1: I got slightly better on the treatment
- 0: The treatment made no difference
- -1: I got worse on the treatment

This is similar to the subjective improvement rating used by Koenig et al. (47). See also Appendix 4: Categorical improvement of Facial Angiofibroma. This will provide data for the following *secondary* efficacy endpoint:

6. Categorical Improvement of Facial Angiofibroma from first visit (V0) after 26 weeks treatment

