10.3.3 Exploratory Efficacy Analyses

The exploratory endpoints, including the change in IGA and FASI from week 26 to follow-up, will be analyzed in the same manner as the appropriate secondary endpoints. The p-values from these comparisons will not be reported but the differences between each dose group and placebo will be summarized as odds ratios or mean differences as appropriate with 95% confidence intervals.

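### For four secondary endpoints an undefined normality check, made on trial data, decides between a stratum-adjusted ANOVA and an unstratified rank test; one test should be fixed in advance

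*Combined protocol and SAP*

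**What the plan says.** Section 10.3.2 groups four of the six secondary endpoints: "The secondary endpoints change in IGA and FASI from baseline to 26 weeks/last assessment, and objective and subject improvement". Their first-line analysis is stated as "These changes will be analyzed using ANOVA including treatment and stratum as main effect fixed factors", with each dose compared with placebo. The next sentence makes that conditional: "If the data is not adequately normally distributed the Kruskal-Wallis non-parametric ANOVA, and Mann-Whitney U tests" take its place. The synopsis repeats the rule.

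The rest of the plan does not complete it:

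- No normality test, cut-off or graphical criterion is named. The plan does not say whether raw values or model residuals are examined, whether the decision is made endpoint by endpoint, or whether it precedes unblinding.
- The rank tests as named have no stratum term. Section 5.3 stratifies randomization by site and three age groups.
- Section 10.3.2 puts the resulting p-values through a Hochberg procedure that it describes as strict control of type I error.
- Section 10.3.2 gives group means, medians and spreads whichever test is used, but no dose-minus-placebo estimate or interval under either branch. Section 10.3.3 does give one for the exploratory endpoints, "summarized as odds ratios or mean differences as appropriate with 95% confidence intervals".
- Section 10.6 requires departures from the plan to be described in the study report. It does not settle which branch is the plan.

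**The concern.** The scales make the condition hard to apply. Patients enter with "An FA severity score of 2 or 3 on the IGA scale" and the scale runs from 0 to 4, so change in IGA takes only a few whole-number values. Change in FASI is also an integer: "The FASI is obtained by summing the partial scores assigned to each of three relevant features of FA for a maximum score of 9". Taken literally, a formal test of whether such data are normal will reject because they are discrete. An effective drug adds to this, because it separates the arms within the pooled values.

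With a literal check, the analysis the plan names first gives way to one that ignores the stratification. With a looser check, or one on residuals, the ANOVA usually stays. Someone makes that choice with the data in hand. At stake are the definition and power of four secondary comparisons per dose, and the meaning of strict error control when an input p-value can come from either of two tests.

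**Working it through.** **The plan's own figure.** The documents give no number for the normality rule. The 40 per group comes from the primary binary endpoint (10% against 40%, α = 0.025) and reproduces with a two-sided test:

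- SE under no difference = √(2 × 0.25 × 0.75 / 40) = 0.0968
- SE under the alternative = √((0.1 × 0.9 + 0.4 × 0.6) / 40) = 0.0908
- Power = Φ((0.30 − 2.241 × 0.0968) / 0.0908) = Φ(0.91) ≈ 0.82, consistent with the stated power above 80%.

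That calculation is unaffected. The checks below use 40 per arm.

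**Possible values.** IGA change runs from 0 − 3 = −3 to 4 − 2 = +2, six values. By Appendix 2, FASI runs from 0 + 0 + 2 = 2 to 3 + 3 + 3 = 9, in whole numbers. The two improvement endpoints differ: raters are "asked to estimate the percentage improvement in the FA lesion appearance from their perspective since baseline (V0". Section 6.1.2 also names these endpoints as four-category ratings and does not say which form is analysed.

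**How often would a check fail?** Simulation, 3 arms × 40, 1,000 trials per scenario, checks at 0.05. Assumed distributions:

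- IGA change −3, −2, −1, 0, +1 with probabilities 0.02, 0.08, 0.30, 0.55, 0.05 on placebo and 0.05, 0.35, 0.35, 0.23, 0.02 on active.
- FASI change: rounded normal, mean −0.5 on placebo and −2 on active, SD 1.0, 1.5 or 2.0.
- Percentage improvement: either 100 × beta(1,4) on placebo and 100 × beta(2,2) on active, or normal with means 30 and 55, SD 20, rounded to 5 and clipped to 0–100.

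| Check | IGA change | FASI change (SD 1.0 / 1.5 / 2.0) | % improvement (two shapes) |
|---|---|---|---|
| Shapiro-Wilk, raw pooled | 100% | 100 / 100 / 94% | 99%, 29% |
| Shapiro-Wilk, residuals, 3 age groups | 83% | 41 / 16 / 9% | 22%, 7% |
| Shapiro-Wilk, residuals, 30 assumed strata | 9% | 8 / 6 / 6% | 6%, 4% |
| Jarque-Bera, residuals (3 age groups) | 2.5% | 5 / 4 / 4% | 3%, 0.3% |
| Absolute skewness or excess kurtosis > 1, residuals (3 age groups) | 0.3% | 2 / 2 / 2% | 0.2%, 0.2% |

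A separate set of runs with 3 or 20 assumed strata gave 100% on raw IGA and FASI change and 5 to 77% on residuals. The branch taken thus depends on details the plan leaves out.

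**Is the switch needed to protect type I error?** Two arms of 40, no effect, nominal two-sided 5%, 20,000 trials:

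| Null case | t-test | Mann-Whitney | Smaller p of the two |
|---|---|---|---|
| IGA, placebo-shaped | 4.8% | 4.7% | 5.8% |
| IGA, active-shaped | 4.8% | 4.8% | 5.4% |
| FASI, SD 1.5 | 4.9% | 4.9% | 5.8% |

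Other assumed shapes, including zero-inflated percentages, gave 5.9 to 6.2% for the smaller p. The stratum-adjusted ANOVA, with or without robust standard errors, stayed at 3.8 to 5.8%.

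**What does the rank branch cost?** Without strata the tests are close: 95.0% (t) against 95.7% (rank) for IGA, and 82.1% against 80.6% for a 1-point FASI difference. The plan's actual pair is stratified ANOVA against unstratified Mann-Whitney. With 3 or 20 strata and between-stratum SD r = 0.3 or 0.6 of the within-stratum SD (all assumed; 3,000 trials per scenario), ANOVA power was 70 to 74% and rank-test power 59 to 70%, a loss of about 4 to 14 points, with different significance verdicts in 7 to 15% of trials. A further set of runs gave a loss of 3 to 16 points and different verdicts in 6 to 16%.

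A hand calculation agrees. Dropping the stratum term multiplies the variance by 1 + r². At 72% ANOVA power the standardized effect is 1.960 + 0.583 = 2.543.

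- r = 0.3: 2.543 / √1.09 = 2.436; power Φ(2.436 − 1.960) = 68%, a loss of about 4 points.
- r = 0.6: 2.543 / √1.36 = 2.180; power Φ(2.180 − 1.960) = 59%, a loss of about 13 points.

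**The case against.** The best defence is that the rule conditions on distribution and not on p-values. Nothing in it lets an analyst run both tests and keep the better one, and a check that always failed would itself fix the test. Both tests hold their level, so little harm follows. This largely stands as regards error rate: even the smaller-p scenario reaches only about 6%. It does not answer the missing criterion or the lost stratum adjustment.

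A reader might go further in three ways that the documents do not support.

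- *The ANOVA will never be used because integer grades always fail.* No check is named, so nothing can be shown always to fail. The claim is nearly true for a formal test on raw IGA and FASI change and often false for residuals or other checks. Nor are the two improvement endpoints, collected as percentages, integer grades.
- *Error control for the secondary endpoints collapses.* The simulated inflation is about one percentage point per comparison at most.
- *The switch leaves four endpoints with no effect size.* Group means and medians are reported either way. Section 10.3.2 promises no between-group estimate under the ANOVA either, and the exploratory endpoints share the same methods yet still get mean differences with intervals. The gap is an unstated effect measure under both branches.

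It is also fair to say that ANOVA is not the only sound choice. A prespecified stratified rank test or ordinal model would remove the data-driven choice equally well.

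**Conclusion.** The point holds in this form: the test for four of six secondary endpoints depends on an undefined check, the plausible versions of that check lead to different tests, and one of those tests drops the stratification. The switch buys no needed protection of the error rate. When it fires it costs about 3 to 16 points of power and changes the significance verdict in roughly 6 to 16% of trials with a drug effect.

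These sizes rest on assumed outcome distributions, an assumed number of strata (the number of sites is not given) and assumed between-stratum variation of 0.3 to 0.6 of the within-stratum SD. With little variation between strata the power loss shrinks to a point or two, and the case is then mainly one of prespecification. This is a cheap improvement to secondary analyses and does not threaten the trial's main conclusion.

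**What to change.** In Section 10.3.2 and in the synopsis:

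1. Delete the sentence that makes the test depend on normality.
2. State that each dose is compared with placebo by the planned ANOVA with treatment and stratum, whatever the distribution, and that the p-value from this model enters the Hochberg procedure.
3. Report the least-squares mean difference with a 95% confidence interval, using heteroscedasticity-robust standard errors.
4. Keep the Mann-Whitney tests for these four endpoints as a labelled sensitivity analysis outside the Hochberg family.

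The same edit should say whether the improvement endpoints are analysed as percentages or as categories.

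Cost: a wording change to the protocol body and synopsis, with no new data, visits or patients. The downside is slightly less power than a rank test if a rating turns out strongly skewed; the sensitivity analysis would show this.
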